## 8.6 Reporting of serious adverse events

All investigators will be thoroughly instructed and trained on all relevant aspects of the reporting obligations for SAEs including the SAEs related to the medical device. This information, including all relevant contact details, is summarized in the investigator site file and will be updated as needed.

SAEs occurring after enrolment up to 30 days after the last study drug administration must be reported within 24 hours of the investigator's awareness. Reports should be as complete as possible, and must be followed up until resolution or stabilization. When required, and according to local law and regulations, SAEs must be reported to the ethics committee and regulatory authorities. If reported, SAEs occurring after the protocol-defined observation period will be processed by Bayer according to all applicable regulations (i.e. notification of Independent Ethics Committees/Institutional Review Boards [IECs / IRBs] and other authorities).

Bayer will inform all investigational sites about the occurrence of suspected unexpected serious adverse reaction/s (SUSARs) according to all applicable regulations.

## 8.7 Expected AEs

The applicable reference document is the most current version of the investigator's brochure (IB) / Company Core Data Sheet (CCDS). Overview listings of frequent events that have occurred so far in the clinical development are shown in the current IB. If relevant new safety information is identified, it will be integrated into an update of the IB and distributed. The expectedness of AEs will be determined by the sponsor according to the applicable reference document and according to all local regulations.

## 8.8 Adverse events of special interest

The following AEs are of special interest:

- Symptomatic hypotension
- Hemoptysis
- Bone and/or growth anomalies

Symptomatic hypotension, hemoptysis as well as bone and/or growth anomalies have been defined as adverse events of special interest and must be documented accordingly in the corresponding adverse events of special safety interest pages in the electronic case report form (eCRF). Events of special interest should not automatically be upgraded by the reporting Investigator to serious. Declaration of an event as serious should only occur when one or more of the serious criterion (as defined in Section 8.1.2) is applicable.

## 8.9 Premature discontinuation of study medication

Subjects must be withdrawn from the study for the following reasons:

- At their own request or at the request of their legally acceptable representative at any time during the study and without giving reasons, a subject may decline to participate further. The subject will not suffer any disadvantage as a result

- If, in the investigator's opinion, continuation of the study would be harmful to the subject's well-being.
- If any AE occurred which is not acceptable in the opinion of the investigator and / or participating parent(s)/legal representative(s) or subject
- Occurrence of adverse drug reactions, which have from the investigator's point of view, a negative impact on the subject's individual risk-benefit ratio.
- If treatment is interrupted for more than 3 days during any individual dose titration phase
- If treatment is interrupted for more than 14 consecutive days during the maintenance phase.
- In case a female subject of childbearing potential is not compliant with pregnancy testing
- In case of lung transplantation
- In case of pregnancy or breast feeding
- In case that the subject fulfills one of the stopping criteria specified in Section 5.1.1
- Subject does not tolerate the lowest possible riociguat dose (0.5 mg TID)
- Patient with pulmonary hypertension associated with idiopathic interstitial pneumonias (PH-IIP)

Discontinuation of bosentan or other ERA treatment (i.e. due to elevated liver enzymes) during the course of the study does not mandate withdrawal of the subject from the study. Also, discontinuation PCA treatment, during the course of the study, does not mandate withdrawal of the subject from the study. The final decision of withdrawal will be the responsibility of the investigator.

The DMC may recommend stopping the trial due to an unfavorable risk benefit assessment during the course of the trial. The final decision to terminate will be the responsibility of the Sponsor.

If the subject or parent(s)/legal representative(s) withdraw(s) consent to treatment with study drug, the investigator will ask to continue with study visits as planned, only with the aim to collect potential study outcomes and AEs. If the subject/parent(s)/legal representative(s) state to the investigator that they no longer authorize to continue to obtain outcome data, this will be respected and documented in the source records, and no further study data will be collected.

In all subjects who prematurely discontinue study drug for other reasons than withdrawal of informed consent, study visits will take place as planned to collect potential study outcomes and AEs.

*(Note the section was modified according to Amendment 6, see Sections 17.3.1.1 and 17.3.1.2.)*

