### Dose titration algorithm

- If systolic blood pressure (SBP) is less than 5 mmHg lower than the age-, sex- and height-adapted level of the 50th SBP percentile (NHBPEP, 2004) (see appendix 18.5), increase riociguat dose (+0.5 mg dose-equivalent TID)

- If SBP is  $\geq 5$  mmHg but less than 10 mmHg lower than the age-, sex- and height-adapted level of the 50th blood pressure (BP) percentile, maintain dose of riociguat.
- If SBP is  $\geq 10$  mmHg lower than the age-, sex- and height-adapted level of the 50th BP percentile, reduce riociguat dose (- 0.5 mg dose-equivalent TID)
- If any SBP is  $\geq 5$  mmHg lower than the age-, sex- and height-adapted level of the 50th BP percentile, with clinical symptoms of hypotension such as dizziness or presyncope, stop study treatment; restart after 24 hours with reduced dose - 0.5 mg dose-equivalent TID).

Down-titration of riociguat is possible for safety reasons at any time point. If at any time, the subject has symptoms of hypotension, temporarily stop the medication and restart after 24 hours with a reduced dose (decrease dosage by 0.5 mg dose-equivalent TID).

The sex- and age-adapted height percentile will be determined using standard height charts (see 18.1, Appendix 1). Age-, sex- and height-adapted levels of the 50th BP percentile will be determined according to [Table 4–1](#) and [Table 4–2](#).

If at any time, the subject has symptoms of hypotension, decrease the dosage by 0.5-mg dose equivalent TID.

At the end of the individual titration period (Visit 4), the subjects should have reached their individually adjusted dose (maximum equivalent dose of 2.5 mg riociguat TID). The established individual equivalent dose will then be taken as optimal dose to be administered during the 16-week maintenance period. Dose reductions for safety reasons are allowed in the maintenance phase, but a subsequent re-increase is not possible. During the LTE phase the dose may be up-titrated at the investigator's discretion.

Subjects not tolerating the body-weight adjusted riociguat 0.5 mg TID will be withdrawn from study.

The respective decision (increase, maintain, decrease) will be entered into the IxRS system. The study medication for the next 2-4 weeks will be dispensed to the subjects.

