### **Dose interruptions**

In the case an interruption takes place during the *individual dose titration period* and lasts longer than 3 consecutive days (9 doses missed), it is not allowed to restart the study medication again (respective subjects must be withdrawn from the trial).

In case an interruption takes place after completion of the titration period and lasts longer than 14 consecutive days, it is not allowed to restart the study medication again. In case of shorter interruptions, study medication can be restarted at the discretion of the investigator. Dose interruptions will be communicated to the DMC and/or SC.

*(Note: The dose titration algorithm, dose up-titration in the LTE phase, and wording under dose interruptions were clarified according to Amendment 9, see Sections [17.4.1.10](#), [17.4.1.6](#) and [17.4.1.9](#).)*

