# 6. Study procedures

## 6.1 Study visits - amended

The main study part comprises 3 periods:

- Pre-treatment period (Screening): up to 2 weeks. This period is to identify potential eligibility of subjects who have been diagnosed with PAH. This visit will take place up to 2 weeks before Visit 1 (baseline visit).
- Main study (Active) treatment period: 24 weeks (titration phase: 8 weeks, maintenance phase: 16 weeks):
  - The individual titration phase comprises 4 visits 2 weeks ( $\pm 2$  days) apart.
  - The maintenance phase comprises 5 visits 4 weeks ( $\pm 5$  days) apart.

- Follow-up period: at least 60 days for serious adverse events (SAEs). (Only for patients who do not enter the long-term extension study or who stop the study medication prematurely.)

Subjects who have completed 24 weeks of treatment will be offered participation in an optional long term extension phase. Subjects not entering the LTE phase will perform the safety follow-up visit (see section 6.1.4). Subjects completing the optional LTE will also perform the safety follow up visit after 60 + 8 days after LTE. Subjects dropping-off the protocol any time after Visit 1 and before Visit 9 will perform an end-of-treatment visit (see section 6.1.3).

The titration visits have to be performed at the study site. Only visits at Week 12 and/or Week 20 (Visit 6 and/or Visit 8) might be performed as home visits by an experienced nurse/ healthcare practitioner in close contact with the treating investigator, when no further titration is scheduled and subjects are on stable dose. The decision to delegate the responsibility to visit the subject is at the discretion of the investigator, must be consistent with regional medical practice, and in accordance with regional legal requirements. The responsibility must be documented on the delegation log and signed by the investigator. At the end of the titration phase (Week 8, Visit 5) patients will have reached riociguat doses between 0.5 mg TID and 2.5 mg TID.

*(Note: The wording describing LTE was modified according to the Amendment 3, see Section 17.1.1.1. The Section was modified according to Amendment 6, see Section 17.3.1.2.)*

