### **6.1.3 End-of-treatment visit - amended**

For all subjects dropping-off the protocol at any time after V1 and before V9, an end-of-treatment visit has to be performed.

The same procedures as at Visit 9 will be performed with the exception of the x-ray of left hand.

In case RHC is conducted based on medical reasons during the study, record RHC parameters to eCRF.

*(Note: The Section was modified according to Amendment 3, see Section 17.1.1.16. The Section was modified according to Amendment 5, see Section 17.2.1.2. This section was modified according to Amendment 9, see Section 17.4.1.13.)*

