### **6.1.4 Safety follow-up visit - amended**

For all subjects stopping study medication either at the end of treatment or prematurely discontinuing the study at any time, a follow-up visit 60 days ( $\pm 8$  days) after last study medication intake has to be performed.

For subjects directly proceeding with treatment in the long-term extension phase, a safety follow-up visit 60 days (+8 days) will be scheduled either at the end of optional LTE phase, when patient's transition to approved and commercially available riociguat in the respective country is possible, or when prematurely discontinuing LTE phase at any time.

The following procedures will be performed:

- Record concomitant medication incl. concomitant PAH specific medication
- Perform physical examination (incl. height, weight and vital signs)
- Pregnancy test for females of childbearing potential
- Check adverse events including adverse events of special interest
- Record laboratory parameters (AST, ALT, BUN, creatinine, GGT, UA, T-Bil, Alb, Na, K, Ca, P, and CBC) to eCRF when obtained as medically required according to a local package insert of bosentan or other ERA, or medical practice at the study site at any time
- In case RHC is conducted based on medical reasons during the study, record RHC parameters to eCRF

*(Note: The safety follow up visit added to concern all subjects as well as the wording was changed according to Amendment 3, see Section 17.1.1.4. The Section was modified*

*according to Amendment 5, see Sections 17.2.1.1 and 17.2.1.2. The section was modified according to Amendment 6, see Section 17.3.1.2.)*

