### **Bone monitoring**

Skeletal development will be assessed throughout the study trial.

During the main study period, x-ray of left hand will be performed before study drug intake (Visit 1) and at week 24 (Visit 9). For those patients entering the extension phase, the x-ray of left hand will be performed every 12 months until growth velocity is plateauing and growth plates are closed.

Bone age and also bone morphology will be determined centrally by a specialist. Every 12 months until growth velocity is plateauing and growth plates are closed, the subject's overall development will also be assessed by physical examination, growth chart evaluation and pubertal development using Tanner scale, and at the discretion of the investigator in case of clinical suspicion for bone and/or growth anomalies.

This data will be reviewed on an ongoing basis by the DMC.

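### Protocol 8.9, two rules in 5.1.1 and SAP 3.2 order withdrawal from the study, while the end of 8.9 and SAP 4.2 keep visits for the same children; under the withdrawal rules an early stopper has no scheduled post-baseline hand X-ray

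*Protocol*

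**What the plan says.** **Rules that order withdrawal.** Protocol 8.9 is titled as premature discontinuation of study medication. Its list of 12 reasons begins "Subjects must be withdrawn from the study for the following reasons". The list includes unacceptable adverse events, treatment interruptions and intolerance of the lowest dose. Section 5.1.1 has two more such rules. Under the titration algorithm, "Subjects not tolerating the body-weight adjusted riociguat 0.5 mg TID will be withdrawn from study". For an interruption of more than 3 consecutive days in titration, "it is not allowed to restart the study medication again (respective subjects must be withdrawn from the trial". SAP 3.2 repeats the rule on intolerance of 0.5 mg.

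**Rules that keep the visits.** Section 8.9 ends: "In all subjects who prematurely discontinue study drug for other reasons than withdrawal of informed consent, study visits will take place as planned". It also asks investigators to continue visits when only consent to treatment is withdrawn. SAP 4.2 repeats both statements and adds that the analysis does not depend on whether the child was taking drug.

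**Other sections on early stoppers.** Section 3.1 says that children who stop drug early will be seen at the safety follow-up visit. Section 6.1 says: "Subjects dropping-off the protocol any time after Visit 1 and before Visit 9 will perform an end-of-treatment visit". Section 6.1.3 defines that visit: "The same procedures as at Visit 9 will be performed with the exception of the x-ray of left hand". Section 6.1.4 sets a visit 60 days after the last dose, "For all subjects stopping study medication either at the end of treatment or prematurely discontinuing the study at any time". None of these four sections says whether Visit 9 is still due.

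**The film.** Under Bone monitoring in 6.2, the main-study "x-ray of left hand will be performed before study drug intake (Visit 1) and at week 24 (Visit 9"). Section 7.4.1 counts the film as part of the primary endpoint.

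**The concern.** A child stopped for an adverse event falls under both sets of rules. One ends the child's participation; the other keeps every remaining visit. Only withdrawal of consent is clearly outside the conflict.

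What is at stake is mainly bone safety. Bone and growth anomalies are an adverse event of special interest (8.8), and section 1.2 reports bone changes in growing rats at 3 to 4 times human exposure. If sites act on the withdrawal wording, post-baseline films in the main study come only from children who reach week 24 in the study. The Data Monitoring Committee's film review in 6.6.2 covers the same group, plus children in the extension. Bone data would then be missing for a reason tied to stopping the drug.

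There is a smaller effect on efficacy. SAP 4.3 defines the last visit as the last post-baseline value, excluding follow-up. For an early stopper that is the end-of-treatment value if the child is withdrawn, and an off-drug Visit 9 value if the child is kept. Two sites could therefore supply different quantities for the same kind of child.

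**Working it through.** The plan states no figure to reproduce, so the check sets the provisions side by side for one child.

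**1. Can study be read as drug throughout?** Not in the Dose interruptions text of 5.1.1. The titration rule bars restarting drug and then adds withdrawal from the trial as a further consequence. The rule for interruptions of more than 14 days after titration bars restarting only. The text therefore treats the two as different acts.

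**2. Scheduled hand films after baseline for a child stopped before Visit 9.**

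| Contact | Film? | Child withdrawn | Child kept |
|---|---|---|---|
| End-of-treatment visit (6.1.3) | excluded | 0 | 0 |
| 60-day safety visit (6.1.4) | not listed | 0 | 0 |
| Visit 9, week 24 (6.2) | yes | not held | 1 |
| **Total** | | **0** | **1** |

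The 12-monthly films in 6.1.6 belong to the extension.

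**3. What is still collected if the child is withdrawn.** The end-of-treatment visit repeats all other Visit 9 procedures: 6MWD, functional class, NT-proBNP or BNP, echocardiography, quality of life, laboratory tests, height, weight and Tanner stage.

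**4. Observation time lost.** Week 24 is day 168. For a stop on day s, the time from the 60-day visit to week 24 is 168 − (s + 60), with a window of ±8 days.

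- s = 28 (week 4): 168 − 88 = 80 days (72 to 88)
- s = 56 (week 8): 168 − 116 = 52 days (44 to 60)
- s = 84 (week 12): 168 − 144 = 24 days (16 to 32)
- The nominal gap is zero at s = 108.

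**5. What missing films could mean.** No discontinuation rate is given, so the losses below are assumptions. With n films and no bone event seen, the one-sided 95% upper bound on the event rate is 1 − 0.05^(1/n).

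| Starting group | Films lost (assumed) | n | Upper bound |
|---|---|---|---|
| 20 (minimum on an ERA) | 0 | 20 | 13.9% |
| 20 | 1 | 19 | 14.6% |
| 20 | 2 | 18 | 15.3% |
| 20 | 4 | 16 | 17.1% |
| 5 (minimum per age cohort) | 0 | 5 | 45.1% |
| 5 | 1 | 4 | 52.7% |

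Overall the loss of precision is small. In a cohort of 5, one lost film is 1/5 = 20% of the bone data.

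**The case against.** The strongest reply is that the plan already resolves the conflict. Section 8.9 is titled for medication, its closing sentence is the specific rule on visits after stopping, and SAP 4.2 repeats it. SAP 4.2 also asks the same children for an end-of-treatment visit and for planned visits, which makes the former additional by implication. Leaving the film out of the end-of-treatment visit fits with taking it at Visit 9. On this view only terminology needs tidying.

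Much of this stands: keeping the visits is the likelier intent. It does not remove the problem. The Dose interruptions rule explicitly orders withdrawal from the trial in addition to stopping drug, and the SAP governs analysis rather than what a site schedules.

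It is also fair that the study is descriptive, that bone and growth anomalies are also reported as adverse events, and that the rat findings were reversible, so a late off-drug film says less. The SAP's phase-wise disposition (6.1.2) and Kaplan-Meier plot of treatment time (4.2) do report stopping treatment separately.

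Four stronger readings are not supported:

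- **That the plan abandons follow-up of early stoppers.** The end of 8.9 and SAP 4.2 say the opposite.
- **That those two places are the only ones on visits after stopping.** Sections 3.1 and 6.1.4, and the consent paragraph of 8.9, also address it.
- **That every remaining planned visit is lost data.** A child stopping at week 4, 8 or 12 has 6, 4 or 3 planned visits left, but those counts ignore the end-of-treatment and 60-day visits still held.
- **That the withdrawal wording shortens time to clinical worsening.** A parenthesis in SAP 6.2.2 names the safety visit as the end of the main phase for children not entering the extension. A child who stopped at week 4 and is kept to Visit 9 could then be censored at integer[(88 + 1)/7] = 12 weeks instead of integer[(168 + 1)/7] = 24. This arises only if visits are kept, and only if the parenthesis overrides the same sentence's definition as the last visit of the main phase. It is a separate, minor clarification.

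**Conclusion.** The contradiction is real, lies in current text, and should be fixed. For a child who stops drug before week 24 without withdrawing consent, the number of scheduled post-baseline hand films is 0 or 1 depending on which sentence the site follows. The net loss per withdrawn child is that film, some interim safety contacts and later off-drug observation. The other Visit 9 data are recovered at the end-of-treatment visit.

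The size across the trial cannot be stated. It depends on how many children stop early and on how sites read the text, and the documents give neither. The conclusion assumes that at least some sites would act on the withdrawal wording.

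**What to change.** **Protocol 5.1.1 and 8.9, SAP 3.2.** Replace withdrawal from the study or trial with *permanently discontinued from study drug*, except where consent to further data collection is withdrawn. The reasons for stopping drug stay as they are.

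**Protocol 3.1 and 6.1.3, SAP 4.2.** State that the end-of-treatment and 60-day safety visits are additional, and that Visit 9 at week 24 with the hand X-ray is kept unless consent is refused or the child is pregnant.

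**SAP 4.2.** Define dropout as leaving follow-up, separately from stopping drug.

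**SAP 6.2.2, minor.** Censor an event-free early stopper who is kept in the study at the later of Visit 9 and the safety follow-up visit.

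**Cost.** One protocol amendment and a SAP revision, wording only. Visit 9 and its film are already scheduled and 8.9 already promises the visits, so no procedure is added. Families of children off drug are asked to attend and to accept one film, which is less informative the longer the child has been off drug. The last-visit value for these children becomes an off-drug value, which SAP 4.2 already accepts.

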## **8.10 Pregnancies**

The investigator must report to the sponsor any pregnancy occurring in a study subject, or in the study subject's partner, during the subject's participation in this study. The report should be submitted within the same timelines as an SAE, although a pregnancy per se is not considered an SAE. The outcome of the pregnancy should be followed up carefully, and any outcome of the mother or child should be reported. For the pregnancy of a study subject's partner, all efforts should be made to obtain similar information on course and outcome, subject to the partner's consent. For all reports, the forms provided are to be used.

## **8.11 Appropriateness of procedures/measurements**

The diagnostic methods to document safety and efficacy outcomes are standard methods in clinical practice and are used and generally recognized as reliable, accurate and relevant.

## **8.12 Device malfunction or failure and medical device related events reporting - amended**

Any device malfunction or failure including use errors or inadequacy in the labeling will be recorded by the clinical/investigational site, including all relevant device information, using the Product Technical Complaint (PTC) form, and forwarded within 24 hours to the Sponsor or Sponsor's designee for evaluation and investigation.

A PTC is any report about a potential or alleged failure of a product in its quality (including the identity, durability, reliability, safety, efficacy or performance) or suspect counterfeit. The complaint may or may not represent a potential risk to the patient.

There are three different situations, in which a PTC form might need to be filled out by the investigator.

1. When an AE is recorded, the investigator needs to check if a device malfunction or failure might be associated with the recorded AE.
2. When a device malfunction or device failure occurs, the investigator needs to assess whether an AE might have occurred in relation to the device complaint.
3. When a device malfunction, device failure, or use error occurs, without any associated AE, this also needs to be captured in the form, especially if it classifies as a near incident, and immediately forwarded to the sponsor for product technical complaints (PTC) investigation.

There are three different categories of medical related events (specified in the PTC form).

